7.1. Primary analysis

Primary between-group comparison will be based on individual-level data rather than cluster-level summaries. Primary comparative analyses will employ a multi-level mixed-effects ordinal logistic regression model to reflect the ordinal nature of the primary outcome and allow for the betweencluster variation (clustering within care homes). A random intercept model will be fitted. The model will adjust for all the cluster-level minimisation factors and individual-level factors including age, sex, and vaccination status (ordinal: no vaccination, partial dose, full dose) as fixed effects. These individual-level factors have been shown to contribute to disparities in fatality rates in COVID-19 patients. The treatment comparison will be presented as an adjusted common proportional odds ratio together with 95% confidence interval, and p-value.

The ordinal logistic regression model is based on the proportionality of odds (parallel lines) assumption, that is, the treatment effect is consistent across the whole composite ordinal primary outcome spectrum. We will test for non-proportionality using a Likelihood Ratio test comparing the model where the coefficients are constrained to be equal across the three log-odds contrasts and the model where the proportional odds assumption is relaxed. If the data sets show significant departures from the proportionality assumption, then an extension of the multilevel ordinal logistic regression model to allow for non-proportional odds will be employed.

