3.1. Trial Design

Multi-centre, open-label, parallel-group, superiority, adaptive platform cluster-randomised controlled trial, allowing up to three interventions to be compared simultaneously with standard care. Interventions may be tested in combination in a factorial design, if appropriate.

Two trial designs may be assessed:

Trial	Prophylactic therapy in care homes trial	Protocol	Final v1.0	date:	13-May-2021	Page:	19 of 44
name:	U1111-1265-4068	version:					

- In pre-exposure prophylaxis (PrEP), care homes will be randomised to IMP versus control once residents have consented to the trial.
- In post-exposure prophylaxis (PEP), care homes will only be randomised to IMP versus control once they have an indication of a developing infection, e.g. recent positive PCR or lateral flow test (or equivalent) in a resident or member of staff (index case).

The choice of whether an IMP should be tested as a PrEP or PEP will depend on multiple factors, including the IMP and its route of administration and cost.

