2.1. Sample size and justification

A total of 530 residents per group are required to detect an odds ratio of 0.67 for a 4-level ordinal primary outcome (no infection proportion 60%, infection remain in CH 15%, all-cause hospitalisation 10%, all-cause mortality 15%), assuming a two-sided significance level of 5% and 90% statistical power, with no adjustment for clustering [2].

Care homes of varying size will be included, and the number of residents recruited per care home will likely be in the range 20–60. Assuming an intra-cluster correlation of 0.11, a coefficient of variation for care home size of 0.49 (Lothian population analysis in 189 care homes[3]) and an average of 32 residents per care home in the study (assuming that the average number of beds per care home is 40[4] and that not all residents will take part in the study), this gives rise to a design effect or inflation factor of 5.25[5].

Therefore, to compare a single active treatment versus usual care, we will need in the region of 174 care homes, i.e., in excess of 5,500 residents. Allowing for the uncertainty surrounding the parameters listed above (e.g. levels of mortality and transmission rates are expected to be different in the second wave due to improved preparedness, better treatments and the potential impact of the expected vaccination programme, therefore it is possible that the observed proportions in the control group may differ), we propose a sample size of 200 care homes and a total number of residents in the region of 6,400 per comparison, with sample size re-estimation during the trial (once 60-day outcome data are available for at least 75% of residents randomised to standard care).

Therefore, comparing three active (unrelated) treatments concurrently versus standard care (in a 1:1:1:1 allocation ratio) would require 400 care homes in total, corresponding to around 13,000 residents.

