Electronic frailty index at 60 days	Electronic frailty index (eFI) The eFI is presented as a score (e.g. if 9 deficits are present out of a possible total of 36 the FI score = 0.25) - higher scores indicate increasing frailty. The eFI score is used to define frailty categories: - Fit (0 - 0.12) - Mild frailty (> 0.12 - 0.24) - Moderate frailty (> 0.24 - 0.36) - Severe frailty (> 0.36) A composite endpoint strategy will be used to handle the eFI outcome truncated due to death by adding an extra category for death to ensure that death equates to the worst outcome.	-	✓	Ordered categorical	Mixed-effect ordinal logistic regression
Ordinal outcome for the most serious event experienced during the 120 days post- randomisation	Four-level ordinal outcome: No SARS-CoV-2 infection, SARS-CoV-2 infection but resident remains in care home, Admission to hospital, all- cause and Death, all-cause.	✓	✓	Ordered categorical	Mixed-effect ordinal logistic regression
Clinical: care home level					

Page **14** of **25**

Written using WPD 16.5 version 3.0, 13-Sep-2018. Effective date: 13-Oct-2018. Template Author: [name]

Outcome measures	Description	Sourc	es	Type of data	Analysis method
Number of SARS-CoV-2 infections in residents in the care home	Aggregate infection rate in the care home. The numerator will be all confirmed SARS-CoV-2 infections including residents not participating in PROTECT-CH trial and the denominator will be the number of residents in the care home at randomisation.	✓	~	Rate (Proportion)	Linear regression (rate difference) and Poisson regression (rate ratio)
Additional Safety:					
Serious Adverse Reactions (SAR, excluding primary and secondary outcomes) and Suspected Unexpected SAR (SUSAR)		✓			
Adverse events relevant to the intervention as specified in relevant IMP specific appendix to protocol		✓			

*For PEP- only applicable for residents not positive at randomisation; [†]excludes residents with directive for no hospitalisation

Page **15** of **25**

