5.2. Baseline characteristics

Baseline characteristics for cluster and individual participant levels will be summarised both overall and by treatment groups using appropriate descriptive statistics for continuous (mean, standard deviation, median, lower & upper quartiles, minimum, maximum and number of observations) and categorical (frequency counts and percentages) characteristics to illustrate balance between the groups at baseline. Baseline summaries will be based on the principal comparisons (between each treatment group and the concurrent standard care group respectively).

Cluster-level characteristics will include:

- Minimisation variables
 - care home type (residential vs nursing vs nursing and residential dual registration)
 - prior COVID-19 in care home at any time (yes vs no)
 - size of care home Total number of residents in care home (small (<30 residents), medium (>30, <50 residents), large (>50 residents))
 - care home has capacity to give oxygen (yes vs no)
- Any residents in care home received vaccination against COVID-19
- Any staff in care home received vaccination against COVID-19
- Country
- Care home ownership
- Registered for clients with learning disabilities
- CQC rating (outstanding, good, requires improvement) or equivalent in devolved administrations.
- Time between positive test for COVID-19 in resident/member of staff and care home randomisation (For PEP only)

Individual resident level baseline demographic and clinical characteristics will include:

- Age
- Sex
- Ethnicity
- BMI (from height and weight)
- Advance directive for no hospitalisation
- Do Not Attempt Resuscitation order
- Smoking status
- Co-morbidities (diabetes, heart disease, chronic lung disease, severe liver disease, severe kidney impairment, dementia, stroke)
- Previous positive test for COVID-19
- Tested positive for COVID-19 at randomisation (For PEP only)
- Received vaccination for COVID-19
- Time in care home
- Electronic frailty index
- Type of consent

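### In post-exposure comparisons, baseline SARS-CoV-2 status is collected but left out of the primary model, and the scoring of residents already positive at randomisation is not settled

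*SAP*

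**What the plan says.** Protocol 3.1 says that in PEP trials "care homes will only be randomised to IMP versus control once they have an indication of a developing infection", and that the index case may be a resident or a member of staff. Protocol 4.1 exempts the index case from the four-week exclusion, and no resident criterion in Protocol 4.2 removes someone who is positive at randomisation. Protocol 1.2 notes that both agents then under consideration were post-exposure.

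The primary analysis set (SAP 4.2 and the opening of SAP 7) is every eligible resident, analysed by the allocation of the home. Beyond the minimisation factors, SAP 7.1 adjusts for "individual-level factors including age, sex, and vaccination status (ordinal: no vaccination, partial dose, full dose) as fixed effects". Protocol 13.2 gives the same covariates as a closed list.

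SAP 5.2 lists, for PEP only, each resident's test status at randomisation and the time from the positive test to randomisation of the home, as baseline descriptors. The footnote to SAP Table 1 restricts time to infection: "For PEP- only applicable for residents not positive at randomisation". No such restriction, covariate or subgroup is attached to the primary outcome.

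The sample size is set "to detect an odds ratio of 0.67 for a 4-level ordinal primary outcome", "assuming a two-sided significance level of 5% and 90% statistical power, with no adjustment for clustering".

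**The concern.** A resident who is infected before Day 0 cannot be kept free of infection by the study drug. For that resident the cut between level 1 and levels 2–4 carries no information about treatment; only the cuts at hospital admission and death do. Pooling such residents with uninfected ones pulls the common odds ratio towards 1. Baseline infection is also likely to be among the strongest predictors of outcome in a PEP trial, so leaving it out gives up precision.

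The SAP recognises the problem for a secondary outcome and does not carry it to the primary one. It also leaves open how these residents are coded: the ordinal level is the worst event in the 60 days after randomisation, and a positive test before Day 0 is not an event in that window. Two analysts could reasonably code the same resident as level 1 or level 2.

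**Working it through.** **1. The plan's own figures.** Inputs from SAP 2.1: control 60/15/10/15%, odds ratio 0.67, two-sided 5%, power 90%, ICC 0.11, CV of home size 0.49, 32 residents per home.

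- Residents per group = 6(z₁+z₂)² / [(ln OR)²(1 − Σp̄³)]. With OR 0.67 the treated distribution is 0.691/0.126/0.077/0.106, and n = 6 × 10.507 / (0.1604 × 0.7255) ≈ 542. With OR 2/3 it is 529.1, which rounds up to the stated 530.
- Design effect = 1 + [(0.49² + 1) × 32 − 1] × 0.11 = 5.255.
- Homes = 2 × 530 × 5.25 / 32 = 173.9, i.e. 174. The plan then takes 200.

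**2. Power at 200 homes with nobody positive.** Effective n per group = 200 × 32 / (2 × 5.25) = 609.5. The standardised effect is 3.2415 × √(609.5/541.8) = 3.438. Power = Φ(3.438 − 1.960) = 93%.

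**3. Assumptions needed.** The share f positive at randomisation is not in the documents. The index-case exemption in Protocol 4.1, read literally, allows at most one known positive per home: 1/32 = 3.1% if it is a participating resident, none if it is a member of staff. The Protocol summary counts the four clear weeks back from the index case, so further positives before randomisation are not clearly shut out. The range shown is 3% to 20%. Also assumed: 60/15/10/15% describes all control residents; positives have 0/55/20/25% and are scored level 2 if they stay in the home; the odds ratio is 0.67 in negatives. In positives the drug has either the same effect on levels 3–4 or none.

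**4. One case by hand, f = 10%.**

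- First cut: negatives not at level 1 are (40 − 10)/90 = 33.3% in control, odds 0.500. Treated odds are 0.335, i.e. 25.1%. The treated mix is 0.9 × 25.1 + 10 = 32.6%, odds 0.483. Against the control odds of 40/60 = 0.667, the ratio is 0.725, not 0.67.
- Second cut, equal effect in positives: negatives at levels 3–4 are (25 − 4.5)/90 = 22.8% in control and 16.5% treated; positives go from 45% to 35.4%. The treated mix is 0.9 × 16.5 + 0.1 × 35.4 = 18.4%, and the ratio against 25% is 0.676.

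**5. Proportional-odds fit to the mixed population, 200 homes.** In each range, the better figure is for an equal effect in positives and the worse for none.

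| Share positive | Common OR | Power |
|---|---|---|
| 0% | 0.67 | 93% |
| 3% | 0.68–0.69 | 90–91% |
| 5% | 0.69–0.70 | 88–89% |
| 10% | 0.71–0.72 | 80–84% |
| 20% | 0.76–0.79 | 55–66% |

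The shortcut Φ(3.438 × abs(ln OR)/0.4005 − 1.960) agrees to about two points. At OR 0.71, for example, it gives Φ(0.98) = 84%.

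**6. Sensitivity to the assumed mix.** If 60/15/10/15% describes negatives only, and positives split 37.5/25/37.5% over levels 2–4, power is 90.4–91.3% at 3%, 84.2–88.2% at 10% and 72.9–84.3% at 20%. Adding baseline status as a simple covariate raises the 10% figure to 87.3–92.7%. With the same split in positives but 60/15/10/15% for everyone, power at 10% is 77.6–82.2% without the covariate and 82.3–89.4% with it. An analysis of negatives only gives 92.2% and 88.8% respectively at 10%.

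**The case against.** The strongest answer is that the primary effect is meant to be that of treating a whole home. Protocol 1.2.2 justifies cluster randomisation by treatment of all residents able and willing. The outcome covers morbidity and death as well as infection, and infected residents can still benefit at the upper levels. That stands: keeping them in gives a valid intention-to-treat effect. A reader might infer bias, or that the primary population must change; the documents support neither.

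A reader might also infer that the planned 90% power is not reached. That holds only above some share positive. At one resident in 32, power at 200 homes is still about 90–91%, because 200 exceeds the 174 calculated. The sample-size text speaks of residents without limiting 0.67 to negatives. If it is the all-resident effect, no dilution was left out of the plan.

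It is tempting to say that proportional odds fails by construction. At 3% the cut-specific odds ratios are 0.685/0.672/0.671 with an equal effect in positives, and 0.685 throughout with none. The gap grows with the share positive (0.725 against 0.676 in step 4), but SAP 7.1 already tests the assumption and names a fallback model.

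SAP 7.2 allows further adjustment for a predictive covariate, which could bring baseline status in. It does so only as a sensitivity analysis and only under marked imbalance, so the primary estimate is unchanged. Finally, an IMP appendix, not among these documents, could handle baseline positives.

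**Conclusion.** The point holds as one of efficiency and definition, for PEP comparisons only. The SAP records a strong baseline predictor, uses it for a secondary outcome and leaves it out of the primary model. It also leaves the coding of a foreseeable group open. The direction is the same in every scenario computed with 0.67 as the effect in negatives: the common odds ratio moves towards 1 and power falls.

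The size cannot be fixed from the documents. It is negligible to small at 3–5% positive and matters from about 10%. It depends on the assumed outcome mix in positives and on 0.67 being the effect in negatives. Under the all-resident reading, only the precision from adjustment is lost. Any statement of how many homes the outbreak-stage covariates would save would need the share of between-home variance they explain, which the documents do not give.

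This is a moderate, free improvement rather than something that must be fixed.

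**What to change.** For PEP comparisons only, in SAP 7.1 and 7.2:

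- State that a resident positive before randomisation who stays in the home, and has no worse event, is level 2.
- Add positive test at randomisation as a pre-specified term, with its own thresholds or as a stratum, because these residents cannot be level 1 and a single shift coefficient does not capture that. Add time from the first positive test to randomisation of the home as a fixed effect.
- Keep the intention-to-treat set as primary, and name a sensitivity analysis in residents not positive at randomisation, matching the Table 1 footnote.

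The cost is SAP wording. Both covariates are in SAP 5.2 and are known before allocation, so the change is clean if made before treatment codes are revealed. The proportion of all residents in the home positive at Day 0 should not be added as a covariate unless derived from participants: Protocol 8.2 schedules only the number of residents at Day 0, and the home-level count of positives at Day 60.

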13.2. Analysis of Outcome Measures

Statistical analyses

The analysis and reporting of the trial will be in accordance with CONSORT guidelines for adaptive and cluster designs [14, 15] with the primary comparative analyses being conducted according to randomised allocation with due emphasis on confidence intervals for between-arm comparisons. All comparative analyses will be based on contemporaneously randomised care homes. A full statistical analysis plan will be developed and agreed with the Platform Steering Committee (PSC) prior to the first release of treatment allocations for final pairwise comparison. The primary approach to between-group comparative analyses will be by intention-to-treat (i.e. according to randomised allocation regardless of adherence to trial allocation). Cluster-level and resident-level descriptive statistics will be used to illustrate balance between the groups at baseline.

Trial	Prophylactic therapy in care homes trial	Protocol	Final v1.0	date:	13-May-2021	Page:	35 of 44
name:	U1111-1265-4068	version:					

Primary comparative analyses will employ a multi-level ordinal logistic regression model including all residents eligible for the intervention of interest prior to care home randomisation. The model will adjust for the minimisation factors, plus the individual-level covariates age, sex and vaccination status. A random effect to adjust for clustering within care homes will be used. The treatment comparison will be presented as an adjusted common odds ratio for a shift in the direction of a better outcome on the ordinal scale together with 95% confidence intervals.[16-19]

Secondary outcomes will be analysed using appropriate regression models dependent on data type (binary, categorical, continuous, time to event etc.), adjusted similarly and accounting for clustering within care homes.

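### SAP 7.1 lets a proportional-odds test on the trial data change the primary model without saying which estimate then decides superiority

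*SAP*

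**What the plan says.** SAP 7.1 fits a random-intercept ordinal logistic model adjusted for the minimisation factors, age, sex and vaccination status. It presents the treatment comparison as one adjusted common odds ratio with a 95% confidence interval and p-value. It describes the proportional-odds assumption as a treatment effect that is the same along the whole scale, and continues: "We will test for non-proportionality using a Likelihood Ratio test comparing the model where the coefficients are constrained to be equal across the three" cuts, against a model that relaxes the assumption. The instruction that follows is: "If the data sets show significant departures from the proportionality assumption, then an extension of the multilevel ordinal logistic regression model" permitting non-proportional odds is to be used.

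These sentences are in the primary analysis section, not among the sensitivity analyses of SAP 7.2. SAP 7 applies no formal adjustment for multiple testing. Protocol 13.2 has no switch: "The treatment comparison will be presented as an adjusted common odds ratio for a shift in the direction of a better outcome". The sample size in SAP 2.1 also rests on one common effect: "A total of 530 residents per group are required to detect an odds ratio of 0.67 for a 4-level ordinal primary outcome".

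**The concern.** A test on the trial's own data decides which model gives the primary result, and four things are left open:

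- the significance level of the test;
- whether it concerns the treatment coefficient or all coefficients;
- whether the common odds ratio remains primary after a significant result;
- which estimate or p-value then decides superiority.

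A significant result is not far-fetched. The lower part of the scale is SARS-CoV-2 infection, while the two worst levels are admission and death from any cause. A drug that works by preventing infection may therefore act more strongly at the first cut than at the others. The trial could end with up to three treatment odds ratios, no stated way to choose between them and no multiplicity control. Its type I error and power would then not be those of the single comparison for which it was sized. The SAP's introduction also aims to let others replicate the analyses, which is not possible for a step with these choices open.

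**Working it through.** **Inputs from SAP 2.1.** Significance and power: "assuming a two-sided significance level of 5% and 90% statistical power, with no adjustment for clustering". Standard-care distribution: "no infection proportion 60%, infection remain in CH 15%, all-cause hospitalisation 10%, all-cause mortality 15" per cent. Clustering: "Assuming an intra-cluster correlation of 0.11, a coefficient of variation for care home size of 0.49", with "an average of 32 residents per care home in the study". Planned size: 200 homes and about 6,400 residents per comparison, so 100 homes and 3,200 residents per arm.

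**Assumptions, because the documents give no figure.** A 5% level for the proportionality test, the cut-specific odds ratios, the success rule after a switch, and an intra-cluster correlation of 0.11 read on the latent logistic scale.

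**Step 1. The plan's own figure.** Whitehead's formula is n per group = 6(z₀.₉₇₅ + z₀.₉₀)² / {(ln OR)² [1 − Σ p̄ᵢ³]}.

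- At OR 0.67 the active-arm proportions are 69.1/12.6/7.7/10.6%, so n = 63.04 / (0.1604 × 0.7255) = 542. At OR 2/3, n = 529. The plan states 530.
- Design effect = 1 + [(1 + 0.49²) × 32 − 1] × 0.11 = 5.255.
- Homes = 2 × 530 × 5.255 / 32 = 174.1.

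The stated figures reproduce. They are for one common odds ratio only.

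**Step 2. Joint distribution of the three log odds ratios.** The cuts are infection or worse (40%), admission or death (25%) and death (15%). Before clustering, the variance at a cut with proportion π is 2 / [3,200 π(1 − π)], which gives 0.00260, 0.00333 and 0.00490. Clustering enters in two ways:

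- Uniform design effect: multiply all variances and covariances by 5.255.
- Shared home intercept, as in the SAP's model: τ² = (0.11/0.89) × π²/3 = 0.407 (here π is the constant); add 2 × 0.407/100 = 0.00813 to every variance and covariance.

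In the second case the home effect cancels from differences between cuts, so the proportionality test is sharper. The three estimates are also more highly correlated (0.84 to 0.92, against 0.51 to 0.73). The proportionality test has 2 degrees of freedom, and 1,000,000 draws were used. The shared-intercept case was checked with full mixed-effects ordinal fits and a treatment-only likelihood ratio test (4,000 null and 2,000 alternative replicates).

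**Step 3. Chance of a switch, treatment-only test at 5%.**

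| Odds ratios at the three cuts | Uniform design effect | Shared intercept | Full fits |
|---|---|---|---|
| 1 / 1 / 1 | 5% | 5% | 4.5% |
| 0.67 / 0.67 / 0.67 | 5% | 5% | 4.2% |
| 0.67 / 0.72 / 0.75 | 11% | 40% | – |
| 0.67 / 0.75 / 0.80 | 21% | 79% | 73% |
| 0.67 / 0.80 / 0.85 | 40% | 99% | – |

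If drug and home effects both act only through infection, full fits switch in 61% (infection OR 0.67) or 90% (0.50). The single random intercept is then misspecified, and the test already rejects in 20 to 30% of trials with no treatment effect.

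**Step 4. Type I error of the two-step procedure.** In the normal approximation the proportionality statistic is independent of the common estimate. So the error = 0.95 × 0.05 + 0.05 × P(success given a switch) = 0.0475 + 0.05 × P.

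| Rule | Uniform design effect | Shared intercept | Full fits |
|---|---|---|---|
| Common odds ratio kept throughout | 5.0% | 5.0% | 5.4% |
| Two-step, any of three | 6.7% | 5.7% | 6.0% |
| Two-step, joint 3-df test | 7.8% | 7.8% | 8.1% |
| Two-step, all three required | 4.7% | 4.8% | – |
| Always switch, any of three | 11.2% | 8.5% | 8.8% |

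A repeat of the shared-intercept any-of-three case gave 5.6 to 5.7%. Even if every switch counted as success, the formula gives 0.0475 + 0.05 = 9.75%. With home effects acting only through infection, the any-of-three rate is 8.7 to 9.6% and the joint-test rate 18 to 27%.

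**Step 5. If all coefficients are tested.** These are full mixed-effects fits with age and treatment relaxed, no treatment effect and 1,000 replicates each (Monte Carlo error about 1 percentage point).

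- Assumed age log odds ratios per SD of 0.05/0.15/0.25: switch in 100%; any-of-three error 9.5%, against 5.3% for the common odds ratio.
- Assumed 0.10/0.15/0.20: switch in 69%; 10.0% against 6.3%.

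**Step 6. Keeping the common odds ratio.** Power at 200 homes is 94% (uniform) to 97% (shared) for OR 0.67, and 89% to 94% for 0.67/0.75/0.80.

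**The case against.** The strongest reply is that the SAP pre-specifies a sensible check and a fallback, and that the alarming readings go beyond its text. Three such readings are tempting, and the documents do not support them as stated.

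- *The common odds ratio is replaced by three odds ratios.* SAP 7.1 promises the common odds ratio without condition and says only that an extension is to be used. It never says the common odds ratio is dropped. An extension that relaxed only covariate terms would keep one treatment odds ratio. The dummy tables that SAP 9 mentions are not in the supplied text, so the planned layout cannot be checked.
- *The switch will probably happen.* Under the plan's own proportional-odds design it happens about 5% of the time with a treatment-only 5% test. Higher figures need assumed level-specific or covariate effects that the documents do not give. The wording of the test does not limit which coefficients it covers, but the sentence before it defines the assumption through the treatment effect. A test of every coefficient is thus possible but not established.
- *False-positive risk nearly doubles.* That needs near-certain switching or misspecified clustering, together with a success rule of any one odds ratio in three. The SAP states no such rule; requiring all three gives slightly under 5%.

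These replies limit the size of the problem. They do not supply the missing test level, scope or decision rule. It is also fair that stating those three items would close the gap without demoting the check, but the primary result would then still depend on a test in the same data.

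**Conclusion.** The point holds as a gap in the primary decision rule, not as a demonstrated doubling of error. The SAP allows a pre-test to change the primary model and does not say what then decides the comparison. Depending on what is assumed for the open choices, two-step type I error runs from just under 5% (all three required) through about 5.6 to 6.7% (treatment-only test, any of three) to about 8% (joint test). It approaches 8 to 11% for any of three only when the switch is nearly always made, for example by testing all coefficients when covariate effects are non-proportional. Misspecified clustering can also raise it. The chance of switching is about 5% under proportional odds and about 20 to 80% for 0.67/0.75/0.80. All these figures rest on an assumed 5% test level and on success rules the SAP does not state; the switching rates above 5% also rest on assumed effects.

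**What to change.** Replace the last two sentences of SAP 7.1 with text to this effect: the adjusted common odds ratio from the mixed-effects proportional-odds model is the primary estimate and the only primary test, whatever the proportionality check shows. Proportionality is examined for the treatment term only and reported descriptively. Odds ratios for infection or worse, admission or death, and death are always presented with confidence intervals as supportive. SAP 7.4 analyses the other ordered outcomes in the same way, so it should follow the same rule.

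This brings the SAP into line with Protocol 13.2 and with the power calculation, and holds type I error at about 5%. It costs wording only and should be settled before treatment codes are revealed.

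The downside is small: under clear non-proportionality the headline is an average shift, which the cut-specific odds ratios beside it explain. Power can be lower than under a looser rule. In the infection-only scenario with infection OR 0.50 it is 74%, against 84% for the two-step any-of-three rule, but that rule's type I error there is 9.6%.
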